### Selection of control areas

Only areas that were untreated and did not qualify for any of the exclusion criteria were entered into the pool of control candidates (Table 2). SL schemes were only introduced in urban areas and rural LSOA11 were accordingly excluded from the matching pool.

Variables (LSOA11-level) for matching were proportions of the population in receipt of income benefits, self-reported non-white ethnicity, and proportions of households from the private rental sector, living in housing in poor condition, overcrowded, or unaffordable, whether buildings were mainly built before 1945 (Table 4). Skewed variables were logarithmically transformed (natural logarithm) prior to matching.

Propensity score matching (PSM) with 1:3 controls and replacement within each super region was used for the treatment (Table 4, Table S4) and spillover units (Table S5-S6) [53].

Table 4 Baseline characteristics for Treated, Never-treated, and propensity score matched control areas (1 treated:3 controls) with replacement. Number of standardised 2011 Lower Layer Super Output Area (LSOA11).

| A
Matching variables | B
Treated | C
Never-Treated | D
Matched Controls | E
Std. dif. (B-D) |
|-------------------------|--------------|--------------------|-----------------------|----------------------|
| THE NORTH               | N=470        | N=7,255            | N=1,410 (967 unique)  |                      |
| Age 0-15 years          | .18          | .19                | .18                   | .06                  |

| Age 16-59 years        | .63   | .58   | .64   | 07   |
|------------------------|-------|-------|-------|------|
| Ln(Income deprivation) | -1.42 | -2.04 | -1.47 | .06  |
| Ln(Private rental)     | -1.58 | -2.19 | -1.57 | 02   |
| Unaffordability        | .93   | 53    | .82   | .06  |
| Ln(Poor housing cond.) | -1.34 | -1.62 | -1.34 | <01  |
| Ln(Overcrowding)       | -2.56 | -3.09 | -2.59 | .05  |
| Ln(Non-White)          | -2.52 | -3.18 | -2.56 | .04  |
| Pre-1945 construction  | .76   | .45   | .76   | <.01 |
|                        |       |       |       |      |

| THE SOUTH              | N=235 | N=13,746 | N=705 (581 unique) |     |
|------------------------|-------|----------|--------------------|-----|
| Age 0-15 years         | .19   | .19      | .19                | 11  |
| Age 16-59 years        | .66   | .58      | .65                | .10 |
| Ln(Income deprivation) | -1.61 | -2.24    | -1.57              | 06  |
| Ln(Private rental)     | -1.37 | -2.08    | -1.42              | .08 |
| Unaffordability        | 1.30  | 11       | 1.21               | .05 |
| Ln(Poor housing cond.) | -1.26 | -1.64    | -1.28              | .07 |
| Ln(Overcrowding)       | -2.10 | -2.90    | -2.15              | .06 |
| Ln(Non-White)          | -1.48 | -2.73    | -1.47              | 01  |
| Pre-1945 construction  | .65   | .35      | .65                | .01 |

| LONDON                 | N=930 | N=3,179 | N=2,790 (1,271 unique) |     |
|------------------------|-------|---------|------------------------|-----|
| Age 0-15 years         | .22   | .19     | .22                    | 06  |
| Age 16-59 years        | .64   | .65     | .64                    | .07 |
| Ln(Income deprivation) | -1.75 | -2.12   | -1.75                  | .01 |
| Ln(Private rental)     | -1.51 | -1.63   | -1.58                  | .11 |
| Unaffordability        | 2.43  | 1.55    | 2.32                   | .08 |
| Ln(Poor housing cond.) | -1.52 | -1.53   | -1.53                  | .03 |
| Ln(Overcrowding)       | -1.59 | -1.87   | -1.65                  | .08 |
| Ln(Non-White)          | 72    | -1.24   | 76                     | .06 |
| Pre-1945 construction  | .76   | .70     | .76                    | .01 |

Data sources: Indices of Multiple Deprivation 2015 [54]; Census 2011 [51]. Abbreviation: Households (hh), Standardised distance (Std. dif.). Regions were defined as The North, The South, and London.

### Variable transformations

We will apply non-linear DID models [55] such as Poisson models for counts or, alternatively, using logit models and dichotomising the specific outcome variables. This way we can avoid the usual approach of log transforming outcome variables, which has implications for the parallel trend assumption [56]. Log transformation would require as-random treatment allocation (not our case) or checking that the outcome distribution is not affected by the intervention itself. Log transformation also affects the interpretation depending on the model, e.g. from measuring additive to multiplicative effects [57].

### Sub-Group Analysis

We will repeat our analyses of individual- and area-level outcomes for the following subgroups:

• Small versus larger SL schemes. We propose this partly because the larger schemes have been politically contentious (following the change of government in 2024, changes were announced to make it easier for LAs to set up large schemes without needing national government permission), and partly because we hypothesise that resident displacement occurs less in larger schemes – particularly where the schemes extend across the whole local authority area. For this purpose, we will define larger schemes as those covering 90%+ of the Local Authority population (Census 2011): 2012\_Newham, 2014\_BarkingandDagenham,

2015\_Croydon, 2015\_Liverpool, 2015\_WalthamForest. Small schemes will in this analysis be defined as those covering up to 20% of the population. Schemes of intermediate sizes will be ignored in this analysis.

London versus outside London. Comparisons with London are useful because it has a unique housing market and some of its areas were settings for the Olympic Games (a potential confounder).

To examine impacts on equity, we will run the following area-level subgroup analyses by ranking local authorities:

- **Level of deprivation**: lower half (least deprived), upper half (most deprived)
- Proportion of population from a Non-White ethnic background: lower half (low proportion), upper half (high proportion)
- **Proportion of population under 16**: lower half (low proportion), upper half (high proportion)
- Proportion of population over 75: lower half (low proportion), upper half (high proportion)

APS includes items that are relevant to the following equity dimensions covered in the PROGRESS+ framework: Place of residence (which we operationalise as region); Ethnicity, Occupation, Gender, Religion, Education as well as participants who live on their own and participants with child dependents. Occupational status and education can be considered proxies for socio-economic status. Furthermore, the survey asks about long term and limiting health conditions, allowing us to consider these dimensions of disability. It also asks about cohabiting same sex partners. We will incorporate these dimensions into the equity analysis where sample sizes allow us to do so.

To address potential multiple testing issues with the secondary analyses, will adjust the significance tests according to a Benjamini-Hochberg False Discovery Rate of 5% [58].

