### Methods

WP1: The proposed impact evaluation uses a difference-in-differences design with matched controls. Individual-level outcomes are self-reported anxiety (primary outcome), wellbeing, general health and residential stability from the Annual Population Survey (APS) and area-level outcomes are an index of mental health and wellbeing (SAMHI: primary outcome), emergency hospital admissions (all cause, cardiovascular, respiratory, asthma, injuries due to falls or burns), ASB, population turnover and rent.

41 Local Authorities operated 61 SL schemes between 2012 and 2019: n=1,635 Lower Layer Super Output Areas (LSOAs); approx. 5.5% of the English population. For our individual-level outcomes, we estimate that the APS includes around 1000 participants per year from these LSOAs. Over our 2012 to 2019 sample period, we expect to observe around 8,000 individuals in the intervention group and three times as many in the matched comparison LSOAs if we match three control LSOAs to every intervention LSOA. We will estimate the average treatment effect on the treated (ATT) using recently developed difference-in-differences methods for staggered treatment adoption.

WP3: We will conduct a cost-benefit analysis using the subjective wellbeing approach to obtain a monetary value for the benefits of SL.

Timeline and Milestones

Start date: 1st December 2023

Length: 26 months.

- 0-3 months: ethics approval, PPI & AG meetings.
- 2-6 months: WP1 update data, submit protocol
- 7-17 months: WP1 Analysis plan and analysis; WP3 prepare data
- 18-22 months: All WPs: Analysis, interpretive workshops; refine and begin write-up
- 22-26 months: final analysis and write-up.

Key words

Housing system; private rented sector, public health, health equity, natural experiment evaluation.

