In 2019, UK government published an independent evidence review of selective licensing, which focused primarily on barriers and facilitators to implementation [9]. We have also searched the literature on health outcomes for housing interventions in PRS. We identified 24 studies, around a third of which focused specifically on selective licensing. These were small-scale evaluations with some useful qualitative findings on implementers' views. There was much less evidence on tenant and landlord views, and no robust quantitative evaluation of the impacts (including health, social and economic impacts) of SL, except for our own recently published evaluation. Our own London study is, to our knowledge, the first and only impact evaluation of SL in the available literature.

Our previous study piloted methods and access to data relevant to this study and found our approach feasible. We found reductions (i.e. improvements) in Small Area Mental Health Index (SAMHI) scores; reductions in police-recorded ASB; and increases in population turnover. The findings are promising but focus on impacts within London's unique housing context. Furthermore, sensitivity analysis revealed that the impacts on SAMHI were driven by changes that occurred in London's largest SL, which was also the main setting for the 2012 London Olympics. The ASB and population turnover impacts remained significant even after we omitted this scheme from the analysis. We also found that although SL schemes have 5-year cycles, impacts began to occur from years 3 to 4. If SL schemes can have important impacts prior to completion, this suggests that the schemes may still be impactful even if they achieve only partial compliance and partial completion. It is important to test if these and other impacts occur at the national level.

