We will explore spillover effects by repeating the difference-in-differences analysis with matching for (1) individuals who do not live in private rented sector housing and (2) for individuals who live in LSOAs that are first-order neighbours of SL areas. For (1) we will compare individuals who do not live in private rented sector housing in SL areas to individuals who do not live in private rented sector housing in the control areas that we have matched to treatment areas for the main analysis. For (2) we will treat the first-order neighbours of treated LSOAs as if they are intervention LSOAs and match

them to comparable LSOAs that are neither SL areas nor SL area neighbours. We will report the average effects over the first five years after the intervention (0 to 5 years) as the main result. We will report this together with an event time plot showing all available years before and after the interventions. In addition, we will report delayed effects and longer-term effects as secondary results.

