| 2018_Brent                    |    |    |    |    | 4   | 39    | 43    | 78,160               |
| 2018_Hackney                  |    |    |    | 1  | 4   | 21    | 22    | 37,890               |
| 2018_Hackney
2018 Harrow   |    |    |    | 1  |     | 14    | 14    |                      |
| 2018_Harrow
2018 Redbridge | 1  |    |    |    | 51  | 40    | 92    | 24,646
168 077    |
| Sub-total                     | 1  | 0  | 0  | 1  | 68  | 860   | 930   | 168,077
1,654,021 |
| วนม-เบเนา                     | 1  | U  | U  | 1  | Jo  | 000   | 230   | 1,034,021            |
| ENGLAND TOTAL                 | 68 | 52 | 15 | 26 | 118 | 1,356 | 1,635 | 2,807,326            |
|                               |    |    |    |    |     |       |       |                      |

Table S2 Selective Licencing Master file variables.

| Number | Variable     | Туре  | Value label | Variable label                  |
|--------|--------------|-------|-------------|---------------------------------|
| 1      | lsoa11       | str9  |             | LSOA11CD                        |
| 2      | la_name      | str22 |             | LA_NAME                         |
| 3      | tyear        | float |             | Year first treated              |
| 4      | cat          | float | cat         | SL classification               |
| 5      | lsoa_area_pc | float |             | (max) Isoa_area_pc              |
| 6      | gor          | str9  |             | Government Region (Aug 2016)    |
| 7      | oslauanm     | str36 |             | Local Authority name (Aug 2016) |

| 8  | nsl             | float  | nsl   | Super Region: North/South/London                       |
|----|-----------------|--------|-------|--|
| 9  | lat             | float  |       | Mean latitude of live small user postcodes (Aug 2016)  |
| 10 | lon             | float  |       | Mean longitude of live small user postcodes (Aug 2016) |
| 11 | tla             | str24  |       | SL scheme 20YY+LA Name                                 |
| 12 | cover           | float  | cover | Treatment area coverage category                       |
| 13 | syear2012       | float  |       | Spillover 2012   |
| 14 | syear2013       | float  |       | Spillover 2013   |
| 15 | syear2014       | float  |       | Spillover 2014   |
| 16 | syear2015       | float  |       | Spillover 2015   |
| 17 | syear2016       | float  |       | Spillover 2016   |
| 18 | syear2017       | float  |       | Spillover 2017   |

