| 19 | syear2018       | float  |       | Spillover 2018   |
| 20 | syear2019       | float  |       | Spillover 2019   |
| 21 | nspill          | float  |       | Number of times a spillover                            |
| 22 | syear           | float  |       | Year first spillover                                   |
| 23 | age0_15         | float  |       | Aged 0-15yr (2011)                                     |
| 24 | age16_59        | float  |       | Aged 16-59yr (2011)                                    |
| 25 | age75           | float  |       | Aged 75+yr (2011)                                      |
| 26 | incomescorerate | float  |       | Income Score (rate)                                    |
| 27 | hh_privaterent  | float  |       | Household tenure: private rented (Census2011)          |
| 28 | hh_poorcond     | double |       | Housing in poor condition indicator                    |
| 29 | hh_overcrowd    | double |       | Household overcrowding indicator                       |
| 30 | hh_afford       | double |       | Housing affordability indicator                        |
| 31 | nonwhite        | float  |       | Non-White (Census2011)                                 |
| 32 | prewar          | float  |       | Built before 1945 (most frequent)                      |
| 33 | urban           | float  |       | Urban 2011 (DEFRA)                                     |
| 34 | cfw             | float  |       | Matched treatment control frequency weight             |
| 35 | scfw            | byte   |       | Matched spillover control frequency weight             |
| 36 | treated         | float  |       | Treatment allocation                                   |
| 37 | prspop11        | int    |       | Census 2011 private rental sector tenants              |
| 38 | pop11           | int    |       | Census 2011 usual residents                            |
| 39 | tla_p           | float  |       | Scheme population% (Census 2011)                       |

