We will apply non-linear DID models [31] such as Poisson models for counts or, alternatively, using logit models and dichotomising the specific outcome variables. This way we can avoid the usual approach of log transforming outcome variables, which has implications for the parallel trend assumption [32]. Log transformation would require as-random treatment allocation (not our case) or checking that the outcome distribution is not affected by the intervention itself. Log transformation also affects the interpretation depending on the model, e.g. from measuring additive to multiplicative effects [33].

Sub-Group Analysis

We will repeat our analyses of individual- and area-level outcomes for the following subgroups:

- Small versus larger SL schemes. We propose this partly because the larger schemes have been politically contentious (following the change of government in 2024, changes were announced to make it easier for LAs to set up large schemes without needing national government permission), and partly because we hypothesise that resident displacement occurs less in larger schemes particularly where the schemes extend across the whole local authority area. For this purpose, we will define larger schemes as those covering 90%+ of the Local Authority population (Census 2011): 2012_Newham, 2014_BarkingandDagenham, 2015_Croydon, 2015_Liverpool, 2015_WalthamForest. Small schemes will in this analysis be defined as those covering up to 20% of the population. Schemes of intermediate sizes will be ignored in this analysis.
- London versus outside London. Comparisons with London are useful because it has a unique housing market and some of its areas were settings for the Olympic Games (a potential confounder).

To examine impacts on equity, we will run the following area-level subgroup analyses by ranking local authorities:

- Level of deprivation: lower half (least deprived), upper half (most deprived)
- **Proportion of population from a Non-White ethnic background**: lower half (low proportion), upper half (high proportion)
- Proportion of population under 16: lower half (low proportion), upper half (high proportion)
- **Proportion of population over 75**: lower half (low proportion), upper half (high proportion)

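### The small-versus-larger scheme comparison mixes scheme size with time since licensing, and the plan sets no rule to separate them

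*Protocol*

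**What the plan says.** The Sub-Group Analysis text is the same in both documents. It defines larger schemes as those covering at least 90% of the local authority population and names them: "2012_Newham, 2014_BarkingandDagenham, 2015_Croydon, 2015_Liverpool, 2015_WalthamForest". For the other arm, "Small schemes will in this analysis be defined as those covering up to 20% of the population", and "Schemes of intermediate sizes will be ignored in this analysis". Neither the small nor the intermediate schemes are listed. The share that decides membership is held in the master file (Table S2, "Scheme population% (Census 2011"), but its values are not given.

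The main analyses are to be repeated in each subgroup. Section 9a, under individual-level outcomes, gives the summary measure: "We will report the average effects over the first five years after the intervention (0 to 5 years) as the main result". It adds an event-time plot, with delayed and longer-term effects as secondary results. The area-level part of section 9a states no window. How group-time effects are to be combined is left open; several aggregation schemes will be applied.

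Protocol section 7b reports from the London pilot: "We also found that although SL schemes have 5-year cycles, impacts began to occur from years 3 to 4". Neither document sets a common follow-up window for the size comparison or mentions that start dates differ by scheme size.

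**The concern.** By the team's own pilot, time since licensing is likely to modify the effect. If one size group is observed mainly in licence years 0-2 and the other through year 4, a pooled post-licensing average describes different stages of the intervention in each. A gap between the averages could then be reported as an effect of scheme size when the schemes work equally well.

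The comparison is pre-specified and is justified by a current policy question (easier approval of large schemes) and by the hypothesis that displacement is less common in larger schemes. A timing artefact could mislead on both.

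**Working it through.** **Inputs.** LSOA counts by scheme and start year come from Table S1, the larger schemes from the Sub-Group Analysis section, and the last outcome year, 2019, from section 18. Event year e is calendar year minus start year.

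**Reproducing the plan's totals.** The Table S1 rows sum to 32 + 14 + 15 = 61 schemes, 1,635 LSOAs (1,356 at 100% coverage) and 2,807,326 people. This agrees with the England total row ("1,356 | 1,635 | 2,807,326") and with the abstract: "41 Local Authorities operated 61 SL schemes between 2012 and 2019: n=1,635 Lower Layer Super Output Areas (LSOAs".

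**Start years (LSOAs, 5-100% coverage).** The reduced set drops the schemes assumed to be intermediate: Nottingham, Redbridge, Brent, Ealing, Hastings and Peterborough. This is an assumption, because authority population shares are not in the documents.

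| Start | Larger | All other | Reduced set |
|---|---|---|---|
| 2012 | 155 | 13 | 13 |
| 2013 | 0 | 10 | 10 |
| 2014 | 110 | 18 | 18 |
| 2015 | 662 | 95 | 50 |
| 2016 | 0 | 77 | 55 |
| 2017 | 0 | 72 | 13 |
| 2018 | 0 | 381 | 111 |
| 2019 | 0 | 42 | 42 |
| Total | 927 | 708 | 312 |

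Reaching e = 4 by 2019 requires a start by 2015; reaching e = 3 requires a start by 2016.
- Larger: all 927 reach e = 4.
- All other: 572/708 = 81% never reach e = 4; 495/708 = 70% never reach e = 3.
- Reduced set: 221/312 = 71% never reach e = 4; 166/312 = 53% never reach e = 3.

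**LSOAs contributing at e = 0, 1, 2, 3, 4, 5.**
- Larger: 927, 927, 927, 927, 927, 265 (sum 4,900).
- All other: 708, 666, 285, 213, 136, 41 (sum 2,049).
- Reduced set: 312, 270, 159, 146, 91, 41 (sum 1,019).

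**Same true effect in every scheme: nil for e < 3, delta for e ≥ 3.**

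*Weighting by LSOA-year* (LSOA-years at e = 3-5 divided by LSOA-years at e = 0-5):
- Larger: (927 + 927 + 265)/4,900 = 2,119/4,900 = 0.43 delta.
- Reduced set: (146 + 91 + 41)/1,019 = 278/1,019 = 0.27 delta; ratio 1.6.
- All other: 390/2,049 = 0.19 delta; ratio 2.3.

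*Averaging within cohort, then by cohort size* (share of observed years 0-5 at e ≥ 3: 3/6 for 2012-14 starts, 2/5 for 2015, 1/4 for 2016, 0 later):
- Larger: (265 × 0.5 + 662 × 0.4)/927 = 0.43 delta.
- Reduced set: (41 × 0.5 + 50 × 0.4 + 55 × 0.25)/312 = 0.17 delta.
- All other: (41 × 0.5 + 95 × 0.4 + 77 × 0.25)/708 = 0.11 delta.

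*Equal weight per event year:* 3/6 = 0.50 delta in every group, so no false difference.

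**Sensitivity.**
- Effect from e = 2, LSOA-year weights: larger 3,046/4,900 = 0.62; reduced set 437/1,019 = 0.43; ratio 1.4.
- Dropping only the four largest other schemes (Nottingham 2018, Redbridge 2018, Ealing 2017, Brent 2018): 66% start in 2016-19, 46% never reach e = 3, and the average is 0.28.
- The 2016-19 share falls below half only if the 11 largest late schemes, and no early one, are dropped.
- 100% coverage only: the other schemes contribute 429, 423, 197, 139, 71 and 3 LSOAs at e = 0 to 5.

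**The case against.** The strongest reply is that the plan does not choose the weighting that creates the artefact. Its main result is framed in event time, and equal weighting of event years gives 0.50 delta in both groups. This stands, and it makes the point conditional. But the plan does not commit to that weighting. Even with it, the small-group estimates at years 3-5 would rest on few LSOAs, all from early starters.

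A second reply is that event-time plots and delayed effects, if repeated by subgroup, would show the pattern. In part they would. Nothing, however, stops the pooled averages being set side by side as the size result, and false discovery rate control does not remove a bias.

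Third, the 0-to-5-year window is stated only for individual-level outcomes. Applying it to area-level outcomes is an inference. LSOA-year weights also only approximate a survey analysis weighted by respondents.

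Fourth, the delayed-effect path comes from a London pilot whose mental health index result was driven by one scheme. The path is an assumption here, and larger schemes are favoured only if effects grow with time.

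A reader might infer that 70% of small-scheme LSOAs cannot reach year 3, or that the distortion is 2.3-fold. Those figures describe all non-large schemes, whereas the plan drops intermediate ones. A reader might also infer that every 2016-19 starter misses the years in which the pilot saw effects. The 77 LSOAs that started in 2016 do reach event year 3, in 2019 only. If the pilot counted the start year as year 1, 2017 starters would reach its year 3 as well.

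**Conclusion.** The point holds in conditional form. The imbalance in start dates is a fact of Table S1: every larger-scheme LSOA reaches event year 4, and 81% of the other LSOAs do not (71% in the reduced set). A false advantage for larger schemes follows if two things hold: effects emerge from about year 3, and years 0-5 are pooled by LSOA-year or by cohort. With LSOA-year weights its size is about 1.6-fold. It is 2.3-fold if all other schemes count as small, and 1.4-fold in the reduced set if the effect starts at event year 2. The reduced set is itself an assumption.

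The documents do not support the stronger reading that the plan must produce a spurious size effect. The defect is an unspecified aggregation rule and the absence of a matched follow-up window. This is a secondary analysis, so the change is advisable and does not affect the primary results.

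**What to change.** State in the SAP that the size contrast is made at matched event years. Use either larger-minus-small differences by event year, or an equally weighted average over event years that both groups adequately reach, with the rule for adequate reach fixed in advance. List the small and intermediate schemes, report the LSOAs and schemes contributing at each event year, and state that a difference in the pooled 0-5 average will not be interpreted as an effect of size.

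A comparison restricted to 2012-2015 starters over years 0-4 is useful only as a sensitivity analysis. It leaves at most 136 non-large LSOAs in 18 schemes, or 91 without Brent and Hastings. At 100% coverage these become 71 and 26, the 26 lying in four schemes.

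The cost is a paragraph in the SAP and a re-aggregation of the same estimates. The price is a wider interval for the size contrast, especially at years 3-4.
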